8. NUMBER OF SUBJECTS

- *Indicate the total number of subjects to be accrued locally. If applicable, distinguish between the number of subjects who are expected to be pre-screened, enrolled (consent obtained), randomized and complete the research procedures.*
- *If your study includes different cohorts, include the total number of subjects in each cohort.*
- *If this is multisite study, include total number of subjects across all sites.*

We will enroll 78 patients in the event that we lose some to follow up or if patients decide to unenroll in the study. We don't foresee many patients being lost to follow up because all patients will be enrolled only until their first follow up visit. The historic rate of patient's not following up with the surgeons after ACL reconstruction is almost 0.

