12. STATISTICAL ANALYSIS

- *Describe how your data will be used to test the hypotheses.*
- *State clearly what variables will be tested and what statistical tests will be used.*

- *Include sample size calculations.*
- *If this is a pilot study, state which variables will be examined for hypothesis generation in later studies.*

Blinding:

Due to the nature of the intervention (bolus block, continuous infusion pump), it is not possible to blind the physicians or patients.

Consent:

Consent will be obtained during the preoperative visit, prior to surgery.

Randomization:

Subjects will be randomly assigned in a 1:1 ratio to either bolus block or continuous catheter. The randomization will be stratified by hospital (Plainview, Franklin, Huntington, Long Island Jewish, or North Shore University Hospital).

The Biostatistics Unit will develop a randomization procedure using a permuted block design within the Biostatistics Randomization Management System (BRMS).

Additional details of the procedure, including required record keeping, will be further developed upon approval of this protocol. The Biostatistics Unit has extensive experience in implementing and in producing detailed documentation for such procedures.

Intention to Treat (ITT):

All analyses will be carried out according to the ITT principle. The ITT population will be all subjects randomized, regardless of what treatment they actually received. All patients will be analyzed in the group to which they were randomized.

Statistical Considerations:**Specific Aims:**

To compare the efficacy of two postoperative pain control methods (bolus block, continuous catheter) in patients undergoing ACL reconstruction.

Primary Outcome

Outcomes measured on post-operative days 0, 1,2,3,4,7, and at the post-operative follow-up visit. (Outcomes for days 0, 1,2,3,4, and 7 will be obtained via email and electronic surveys . Outcomes for the post-operative follow-up visit will be measured during the postoperative visit which takes place between days 10 and 14. This will be referred to as "Day 10").

- Pain Control

- Maximum pain will be measured on a scale of 0 to 10, where 0 represents no pain and 10 represents the worst possible pain. Patients will report the maximum pain felt in the 24 hours
- Current pain will be measured on a scale of 0 to 10, where 0 represents no pain and 10 represents the worst possible pain.
- Daily opioid consumption (expressed as morphine equivalents).

Secondary Outcomes

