- e. In addition, the patients will be on a monitor in the post anesthesia recovery unit until they are deemed stable and ready for discharge. Any abnormalities will be noted by the nurse taking care of the patient who would inform the anesthesiologist

and surgeon. This is standard protocol at our institution when any regional blocks are given for post-operative patients.

- f. The patients will be given a hand out and instructed to watch for signs or symptoms such as chest pain, rapid heart beating, difficulty breathing, or seizure like activity. If any of these symptoms are present, they would normally be observed immediately after the block is performed or while the patient is still being monitored, however after discharge they will still be informed to watch for symptoms in the event of a delayed response. They will be instructed to call the study PI or safety officer and likely be sent to the emergency room for evaluation.

Unanticipated events will be assessed on a case by case basis and the study investigators will determine if the patient should be halted/discontinued and whether or not they should seek immediate care.

Any participant who is discontinued from treatment will continue to be assessed following the previously stated follow-up procedure.

The data to be collected at the time of study intervention discontinuation will include the following:

- All data pertaining to the patient's enrollment in the study including which arm of the study they were randomized to, whether or not they received the treatment to which they were randomized, all outcome data that was recorded up to the time of discontinuation and any stated reason for discontinuation will be documented.
- Should a participant experience a known complication of the medication this will be recorded as an adverse event, serious adverse event, or unanticipated event as noted above.
- The participants will continue to be followed according the protocol and their outcome data will continue to be obtained as is possible given the situation.
- A case report form page will be produced for any participant who discontinues treatment or withdraws, this will include the date and any specific reasons for discontinuation/withdrawal from the study.

Participants are free to withdraw from participation in the study at any time upon request.

An investigator may discontinue or withdraw a participant from the study for the following reasons:

- Serious adverse event
- Pregnancy

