- Significant study intervention non-compliance

- If any clinical adverse event (AE), laboratory abnormality, or other medical condition or situation occurs such that continued participation in the study would not be in the best interest of the participant. Adverse events or unanticipated events will be assessed on a case by case basis and discontinued as noted in the section above.
- If the participant meets an exclusion criterion (either newly developed or not previously recognized) that precludes further study participation.
- An investigator will discontinue/withdraw a patient from study participation if they are not deemed contactable, this will be defined as inability to contact after 3 separate attempts are made at least 2 hours apart across two days.

The reason for participant discontinuation or withdrawal from the study will be recorded on the Case Report Form (CRF) as noted in the section above. Subjects who sign the informed consent form and are randomized but do not receive the study intervention they are randomized to will be followed in the study as if they have obtained their intervention this deviation from protocol will be documented for post-hoc analysis reasons. Subjects who sign the informed consent form, and are randomized and receive the study intervention, and subsequently withdraw, or are withdrawn or discontinued from the study, maintained in the group to which they are randomized for assessment documentation with notation made as to their withdrawal to assist in the post-hoc analysis.

Study participants who are randomized to the continuous infusion cohort will be provided with information about the pumps themselves and troubleshooting advice. They will also be provided with contact information for the investigators should they run into issues. The troubleshooting of the device will be done as noted in the above section and need for discontinuation of the therapy will be assessed as noted above with safety concerns as the primary reason for discontinuation.

A participant will be considered lost to follow-up if he or she fails to respond to study surveys followed for more than one day of follow up, misses the phone calls, or misses the post-operative office visit planned for postoperative day 10-14 and is unable to be contacted by the study site staff.

The following actions must be taken if a participant fails to respond to study surveys or return to the clinic for a required study visit:

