- The investigators will attempt to contact the participant and reschedule the missed visit planned for Post-op days 10-14 and counsel the participant on the importance of maintaining the assigned visit schedule and ascertain if the participant wishes to and/or should continue in the study.
- Before a participant is deemed lost to follow-up, the investigator or designee will make every effort to regain contact with the participant

(where possible, 3 telephone calls and, if necessary, a certified letter to the participant's last known mailing address or local equivalent methods).

These contact attempts will be documented in the participant's medical record or study file. After 3 attempted phone calls spanning two postoperative days the patient will be deemed lost to follow-up.

- Should a participant be unreachable for one day of the study follow-up this will not be deemed a loss to follow-up, however this occurrence will be documented in the data and accounted for in the analysis phase of the study.

Should the participant continue to be unreachable, he or she will be considered to have withdrawn from the study with a primary reason of lost to follow-up.

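### Section 16 contradicts itself on patients who cannot be reached; read literally, its two-day rule can stop collection of later outcome and adverse-event data that are still obtainable

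*Combined protocol and SAP*

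**What the plan says.** Section 16 deals with unreachable patients in several places.

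- The list of withdrawal grounds opens permissively: "An investigator may discontinue or withdraw a participant from the study for the following reasons".
- One bullet in that list is mandatory: "An investigator will discontinue/withdraw a patient from study participation if they are not deemed contactable". Its definition is "this will be defined as inability to contact after 3 separate attempts are made at least 2 hours apart across two days". The mode of contact is not named.
- The lost-to-follow-up text sets out steps for a patient who misses surveys or the clinic visit. Before loss is declared, staff are to try hard to regain contact, where possible by "3 telephone calls and, if necessary, a certified letter". The same steps then state: "After 3 attempted phone calls spanning two postoperative days the patient will be deemed lost to follow-up". One unreachable day is not loss to follow-up, but a longer silence is treated as withdrawal, with loss to follow-up as the reason: "Should the participant continue to be unreachable, he or she will be considered to have withdrawn from the study with a primary reason of lost".
- Continued follow-up is promised to patients who withdraw from a study arm (unless they decline contact) and to patients discontinued from treatment. Withdrawn patients stay in their randomized group, with the withdrawal noted.

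Section 12 (Statistical Analysis) gives the source of the primary outcomes: "Outcomes for days 0, 1,2,3,4, and 7 will be obtained via email and electronic surveys". The last assessment is made in person at the POD 10-14 visit. The phone calls on POD 1, 2, 3, 4 and 7 are for adverse events (Sections 6 and 11). On attendance, Section 8 says: "The historic rate of patient's not following up with the surgeons after ACL reconstruction is almost 0". Section 12 makes no drop-out allowance, on similar grounds.

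**The concern.** A patient can be unreachable for two days after surgery and then respond again. If the mandatory bullet is followed, that patient leaves the study early, and nothing in the protocol says that the remaining surveys, calls and visit still take place. Temporary silence then becomes permanent missing data.

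Two features raise the stakes. First, the trial is open-label and analysed by intention to treat. Early silence may be related to pain, opioid sedation or a complication, so the missing values may be informative. That link is plausible, but the documents do not establish it. Keeping a patient in the randomized group does not supply values that were never collected. Second, the infusion runs for 48-72 hours. Withdrawal around POD 2 could end the planned adverse-event calls on POD 3, 4 and 7 while a catheter patient is still infusing or has only just finished.

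**Working it through.** **1. The statements in Section 16 compared**

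| Question | One statement | Another statement |
|---|---|---|
| Is withdrawal for non-contact required? | List stem: the investigator *may* withdraw | Bullet: the investigator *will* withdraw |
| When is a patient lost? | After calls and, if needed, a certified letter | After three calls over two postoperative days |
| Does data collection go on afterwards? | Yes, after leaving a study arm or stopping treatment | Nothing is said for withdrawal as uncontactable |

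A certified letter cannot realistically be sent, received and answered within two days, so the two answers in the second row cannot both be followed.

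**2. Assessments at risk**

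From POD 1 onward there are 6: POD 1, 2, 3, 4, 7 and the POD 10-14 visit. If withdrawal follows two silent days, those still to come are:

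- silent POD 1-2: POD 3, 4, 7 and the visit = 4 of 6
- silent POD 2-3: POD 4, 7 and the visit = 3 of 6
- silent POD 3-4: POD 7 and the visit = 2 of 6

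These are upper limits, because a patient who would have stayed silent anyway loses nothing through the rule.

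**3. The plan's own sample size**

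Inputs from Section 12: difference 2 points, SD 2.5, two-sided alpha 0.01, power 80%, 1:1 allocation, no drop-out allowance.

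- Standardized difference: 2 / 2.5 = 0.8.
- Normal approximation: n per group = 2 × (2.576 + 0.842)² / 0.8² = 36.5, rounded up to 37.
- Exact two-sample t-test: 38.19, rounded up to 39 per group, with power 81.0%.

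The stated 39 per group (78 in total) is reproduced and is not in dispute.

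**4. Single-day power with fewer patients**

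This uses the same t-test, with noncentrality 0.8 × √(n/2) and 2n − 2 degrees of freedom.

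| n per group | Noncentrality | Power |
|---|---|---|
| 39 | 0.8 × √19.5 = 3.53 | 81.0% |
| 38 | 0.8 × √19 = 3.49 | 79.8% |
| 37 | 0.8 × √18.5 = 3.44 | 78.4% |

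**5. What would produce those losses (assumptions only)**

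The planning difference comes from day 3 of a shoulder-surgery trial. On day 3, only silence on POD 1-2 can cost data through the rule. Assume that 5% or 10% of patients are unreachable on any given day:

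- A silent day is followed by another half the time, 5%: 0.05 × 0.5 × 78 = 1.95, about 2 patients, so 38 per group and 79.8%.
- The same persistence, 10%: 0.10 × 0.5 × 78 = 3.9, about 4 patients, so 37 per group and 78.4%.
- Independent days, 10%: 0.10 × 0.10 × 78 = 0.78, less than one patient, and power of about 80.5%.

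Losses are taken as equal in the two arms.

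**The case against.** The strongest defence is that Section 16 is untidy rather than harmful. It stands on several points.

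- A reader might infer that withdrawal is compulsory. The list stem is permissive, one unreachable day does not count, and further contact efforts come before loss is declared. Compulsion is one reading of a conflict. The permissive reading is no remedy, though, because it leaves withdrawal to investigators who know the treatment arm.
- A reader might infer that a patient who answers surveys but not the phone is removed. The text does not establish this. The three calls are steps for someone who has already missed surveys or the visit, the loss definition also requires that staff cannot reach the patient, and Section 7 treats contact as telephone and/or e-mail. Section 6 adds two-hourly survey reminders and staff notifications. Removing a survey responder is only a possible reading.
- A reader might infer that data are thrown away. Nothing says so: collected values stay in the randomized group and the analysis is by intention to treat.
- A reader might charge every patient with any two-day silence in POD 1-4 to one day's test. With persistence, that is about 4 of 78 at 5% (37 per group, 78.4%) and 8 of 78 at 10% (35 per group, 75.5%). This overstates the effect on day 3, for the reason given in step 5.
- Section 11 records adverse events for 7 days, and serious ones for 30 days, after participation ends, and calls to a silent patient protect only so much. This tempers the safety argument but does not remove it. If withdrawal on POD 2 counts as the end of participation, the non-serious window closes on POD 9 (2 + 7), before the POD 10-14 visit.

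The defence does not answer the gap itself: no sentence says that surveys, calls and visit outcomes continue for a patient withdrawn as uncontactable.

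**Conclusion.** The point holds as an internal contradiction with a practical consequence. Section 16 does not say consistently whether two days of non-contact ends participation, and its promises of continued follow-up do not extend to patients withdrawn on that ground. Read literally, the rule can stop collection of up to 4 of the 6 assessments from POD 1 onward, together with the adverse-event calls, in a population that the protocol expects to return to the surgeon almost without exception.

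The effect on power is small and illustrative: from 81.0% to 79.8% or 78.4% if one or two patients per group are lost on a given day. It rests on assumed non-response rates, since the documents give none. It matters only because there is no drop-out margin, so one loss per group already takes single-day power just below the planned 80%. The main reasons to act are the contradiction, avoidable and possibly informative missing data, and adverse-event follow-up. This should be corrected. It does not invalidate the design or the sample-size calculation.

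**What to change.** Reconcile the statements in Section 16 on withdrawal from a study arm, discontinuation of treatment, the list of withdrawal grounds and loss to follow-up, so that two days of non-contact is no longer a ground for ending data collection. State that:

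- non-response on any day is recorded as a missed assessment;
- the remaining REDCap surveys are still sent, the planned calls are still attempted, and outcomes and adverse events are still collected at the POD 10-14 visit, unless the patient declines further contact;
- lost-to-follow-up status is assigned only after the final survey and the visit have both been missed and the contact steps already listed in Section 16 have failed.

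The cost is a wording change. Survey reminders are automatic, the calls are already planned and the visit is routine care. The only downside is a few extra call attempts to non-responders.

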17. RISKS TO SUBJECTS

- *Describe any potential risks and discomforts to the subject (physical, psychological, social, legal, or other) and assess their likelihood and seriousness and whether side effects are reversible. Where appropriate, describe alternative treatments and procedures that might be advantageous to the subjects.*
- *Include risks to others , like sexual partners (if appropriate)*
- *Discuss why the risks to subjects are reasonable in relation to the anticipated benefits and in relation to the importance of the knowledge that may reasonably be expected to results*
- *Describe the procedures for protecting against or minimizing any potential risks, including risks to confidentiality, and assess their likely effectiveness.*

Risks associated with single shot adductor canal block

4. Peripheral Nerve Injury

- a. This is a rare complication that is usually transient and goes away with time. The estimated incidence is .5% for any nerve irritation after the procedure. The risk of injury to the nerve that is permanent in 1/10,000. These are very rare in part due to the implementation and success of ultrasound use for guidance of the needle and/or catheter during nerve blockade. This allows the anesthesiologist direct visualization to differentiate between perineural, intraneural, and interfascicular.
- b. These injuries will be monitored with a physical examination after the procedure once the patient has woken from anesthesia. Any deficits beyond what is expected by the nerve blockade will be followed at post-operative visit in the office to evaluate for resolution of transient symptoms. In the event of a peripheral nerve injury there is no intervention that can change the outcome of the block that has been delivered. If symptoms fail to progressively improve, neurological consultation should be sought in 3-4 weeks. Incomplete lesions with evidence of moderate or severe deficit are an indication for early neurological consultation and consideration of neurophysiologic testing (nerve conduction studies and electromyography).

5. Local Anesthetic System Toxicity

- a. Ranges from mild symptoms of metallic taste, agitation, and circumoral numbness to more severe findings such as seizure, respiratory arrest, cardiac arrhythmias.
- b. Manifestations of local anesthetic toxicity typically appear 1 to 5 minutes after the injection, but onset may range from 30 seconds to as long as 60 minutes. These symptoms will be monitored for and usually happen because of accidental injection into the vascular system. This is exceedingly rare with the advent of ultrasound guidance and direct visualization of the injection. During the procedure the patients are attached to full monitors which will monitor blood pressure, cardiac rhythm, oxygen saturation. Any noticeable severe findings are treated with supportive care with propofol, lipid infusions which can reverse the effects from the local anesthesia.
- c. Lipid infusion protocol as recommended by the ASEA practice advisory on local anesthetic systemic toxicity is as follows:
 - i. 1.5 ml kg⁻² bolus of 20% lipid emulsion Infusion at 0.25 ml kg⁻² per min for at least 10 min after return of circulatory stability Consider giving a second bolus and increasing infusion to 0.50 ml kg⁻² if circulatory stability not attained Upper limit of lipid emulsion recommended is 10 ml kg⁻² over the first 30 min.
- d. In addition, the patients will be on a monitor in the post anesthesia recovery unit until they are deemed stable and ready for discharge. Any abnormalities will be noted by the nurse taking care of the patient who would inform the anesthesiologist and surgeon. This is standard protocol at our institution when any regional blocks are given for post-operative patients.
- e. The patients will be given a hand out and instructed to watch for signs or symptoms such as chest pain, rapid heart beating, difficulty breathing, or seizure like activity. If any of these symptoms are present, they would normally be observed immediately after the block is performed or while the patient is still being monitored, however after discharge they will still be informed to watch for symptoms in the event of a delayed response. They will be instructed to call the study PI or safety officer and likely be sent to the emergency room for evaluation.

6. Local Infection

- a. For single shot adductor canal blocks the risk of infection is very low. To minimize this risk the site is prepped in sterile fashion with either chlorhexidine or iodine scrub. The injecting physician washes hands and uses sterile gloves and instruments for the course of this procedure.

- b. Perioperative antibiotics will also be given which is standard protocol for ACL reconstruction regardless of catheter insertion or not.
- c. In the event that the patient notices any skin irritation, redness, foul smell, or drainage from the site of the injection, they will be advised to first call the safety officer, PI, or other co-investigator to describe their symptoms. The patients will also watch for fevers or chills. If infection is suspected they will be sent to the emergency room or surgeon's office for evaluation and further testing. They may be started on a course of oral antibiotics if an infection is concerning after evaluation.

Risks associated with continuous peripheral nerve catheter placement:

- 6. Both anesthetists and surgeons recognize the benefits of peripheral nerve catheters (PNCs). The continuous infusion of local anesthetic near a peripheral nerve or plexus produces fewer systemic side-effects than i.v. opioids, increases postoperative patient satisfaction, and can allow for faster functional recovery of the operated limb.
- 7. Block Failure
 - a. Occasionally, there are instances when the catheter is passed easily but the nerve block fails to provide adequate anesthesia or analgesia.
 - b. This is rare with the use of ultrasound guidance and localization of the continuous catheter.
 - c. In the event of a block failure or inadequate placement that is not providing the patient any relief, the catheter will be removed either by the patient or post operatively depending on when it is discovered.
 - d. The practicing anesthesiologist will discuss with the patient the option of either trying a second time to place the catheter successfully in the post anesthesia recovery area or discontinuing the block altogether.
- 8. Accidental Catheter Migration/Removal
 - a. The incidence of accidental catheter removal is reported in the literature at about 1%. The use of sterile adhesive tagaderm dressing has been implemented to firmly secure the catheter to the skin to avoid migration or fall out. The dressing is checked to be secure after it has been applied.
 - b. In the event that the catheter is accidentally removed or dislodged during the course of the study, it should be removed and there will be no further intervention once the patient has been discharged home. The patient can place a Band-Aid over the catheter site and notify the coinvestigator or PI.
- 9. Localized Infection

- a. Localized inflammation is infrequent (0–10%), and local infection (0–3%), abscess formation (0–0.9%), and sepsis occur even more rarely.
- b. Transparent dressings are used to reduce the number of dressing changes while appropriately monitoring the site for signs of inflammation
- c. Since the continuous catheter remains in for 48-72 hours, it does pose a theoretical increased risk of infection compared to a single shot adductor canal block although this has not been proven in the literature. To minimize this risk the site is prepped in sterile fashion with either chlorhexidine or iodine scrub. The injecting physician washes hands and uses sterile gloves and instruments for the course of this procedure.
- d. Perioperative antibiotics will also be given which is standard protocol for ACL reconstruction regardless of catheter insertion or not.
- e. In the event that the patient notices any skin irritation, redness, foul smell, or drainage from the site of the injection, they will be advised to first call the safety officer, PI, or other co-investigator to describe their symptoms. The patients will also watch for fevers or chills. If infection is suspected they will be sent to the emergency room or surgeon's office for evaluation and further testing. They may be started on a course of oral antibiotics if an infection is concerning after evaluation

10. Local Anesthetic System Toxicity

- a. The patients with a continuous catheter will be receiving a fixed rate of flow of local anesthetic to the nerve site for 48-72 hours. This does put them at a theoretical risk for toxicity while they are at home with the catheter in even though the dosage is well below the threshold for systemic toxicity. They will be educated on the following signs and symptoms similar to the single shot patients.
- b. Ranges from mild symptoms of metallic taste, agitation, and circumoral numbness to more severe findings such as seizure, respiratory arrest, cardiac arrhythmias.
- c. Manifestations of local anesthetic toxicity typically appear 1 to 5 minutes after the injection, but onset may range from 30 seconds to as long as 60 minutes. These symptoms will be monitored for and usually happen because of accidental injection into the vascular system. This is exceedingly rare with the advent of ultrasound guidance and direct visualization of the injection. During the procedure the patients are attached to full monitors which will monitor blood pressure, cardiac rhythm, oxygen saturation. Any noticeable severe findings are treated with supportive care with propofol, lipid infusions which can reverse the effects from the local anesthesia.

d. Lipid infusion protocol as recommended by the ASEA practice advisory on local anesthetic systemic toxicity is as follows:

- i. 1.5 ml kg⁻¹ bolus of 20% lipid emulsion Infusion at 0.25 ml kg⁻¹ per min for at least 10 min after return of circulatory stability Consider giving a second bolus and increasing infusion to 0.50 ml kg⁻¹ if circulatory stability not attained Upper limit of lipid emulsion recommended is 10 ml kg⁻¹ over the first 30 min.
- e. In addition, the patients will be on a monitor in the post anesthesia recovery unit until they are deemed stable and ready for discharge. Any abnormalities will be noted by the nurse taking care of the patient who would inform the anesthesiologist and surgeon. This is standard protocol at our institution when any regional blocks are given for post-operative patients.
- f. The patients will be given a hand out and instructed to watch for signs or symptoms such as chest pain, rapid heart beating, difficulty breathing, or seizure like activity. If any of these symptoms are present, they would normally be observed immediately after the block is performed or while the patient is still being monitored, however after discharge they will still be informed to watch for symptoms in the event of a delayed response. They will be instructed to call the study PI or safety officer and likely be sent to the emergency room for evaluation.

Unanticipated events will be assessed on a case by case basis and the study investigators will determine if the patient should be halted/discontinued and whether or not they should seek immediate care.

Since identifiers are being recorded, there is also risk of loss of confidentiality of the patients

